## Recruitment Feasibility and Retention

### Recruitment

We intend to recruit 453 cigarette smokers over a 40-month period (60 months – 4 months for prep – 12 months for final follow-up – 4 months for data cleaning/analysis). We have already recruited approximately half of the sample in Oklahoma (n=220); therefore, we plan to recruit an additional 233 participants from the Columbus, Ohio area. The adult population of the Columbus Metropolitan Area is  $\sim 2,078,725$  (US Census estimate, 2017) and 22% of Columbus residents smoke. Given that EC use is expected to rise over the next several years we conservatively estimate an average rate of trying at 50% for the proposed study duration. Therefore, our pool of potential participants in our local area is 228,660 ( $2,078,725 \times .22 \times .50$ ). Because we

### Examination of First and Second Generation E-cigarettes

are trying to enroll 453 participants (0.002% of our potential pool) over a 40-month period, we are confident that our recruitment approaches will yield sufficient numbers and in our ability to enroll ~11 smokers per month (453/40 months).

#### **Retention**

All participants will receive \$5 per visit to offset travel costs except those who utilize Lyft transportation services provided at no cost by the research team to and from the study site for 8 visits (\$40), receive \$7, when applicable, for parking, \$40 for visit 1 and \$20 for each subsequent visit after that in which they attend (\$180), an additional \$20 for visits when specimens are collected (\$100), \$1 for each online diary entry (\$105 possible) and an additional bonus up to \$100 for protocol compliance (attending  $\geq$  7 visits and completing  $\geq$ 70% of online daily diary entries, and returning study products) for a total up to \$505. The bonus payment will be given at different time points to encourage participant engagement: \$5 will be given at weeks 1, 4, 8, and 12 if the participant returns their study product for a total of \$20 and the remaining \$20 will go towards their bonus of completing their product phase at their week 12 visit. To receive the \$5 that went towards the completion of the product phase at weeks 1, 4 and 8 visits, participants will need to attend the week 12 visit. The remaining \$40 will be compensated at week 52 if the participant attended  $\geq$  7 visits and completed  $\geq$ 70% of online daily diary entries. If an entire study visit is not able to be completed, the participant will be compensated \$5 for travel and, if applicable, \$7 for parking. We will also facilitate study visits by offering evening and weekend appointments as well as additional retention strategies (e.g., multiple sources of contact, reminder calls/texts/emails). To improve engagement and retention of study participants, participants will receive reminder calls in addition to email or text reminders. Reminders will be sent by text or email based on a participant's preferred method of contact. The participant's preferred method of contact for communication will be observed; however, alternative methods may be employed if issues arise with the preferred method (e.g., participant has run out of minutes; cellular providers are not compatible). These methods are consistent with our team's previous studies and have resulted in excellent retention rates.

#### **Project Timeline**

Months	Year 1			Year 2			Year 3			Year 4			Year 5		
	1-4	5-8	9-12	1-4	5-8	9-12	1-4	5-8	9-12	1-4	5-8	9-12	1-4	5-8	9-12
Preparation; supplies; training; IRB approval	X														
Recruitment & Enrollment		X	X	X	X	X	X	X	X	X	X				
Follow-ups		X	X	X	X	X	X	X	X	X	X	X	X	X	
Data analysis, report writing, dissemination															X

#### **Detailed Study Procedures**

Advertisements will direct interested potential participants to complete a secure, online screener. Information regarding eligibility and the participants' email addresses and phone numbers will be uploaded into a secure database. Potential participants will then be further screened by phone.

## Examination of First and Second Generation E-cigarettes

**Phone Screening:** Trained staff will provide a brief description of the study and for those still interested, schedule an orientation and assessment visit and provide directions to the study site. No cost ride services through Lyft will be discussed as an option for participants who may not have reliable means of transportation.

**Orientation and Assessment Visit:** During this first visit, participants will be informed of the study procedures and rationale and asked to provide informed consent. To ensure eligibility, participant smoking status will be biochemically confirmed via exhaled carbon monoxide testing ( $CO \geq 4$  ppm) and eligibility related questions will be asked again and responses verified. Pregnancy exclusion will also be confirmed with a urine test (n.b., pregnancy tests will be completed at each visit throughout the study). Participants will provide basic demographic and smoking history information consistent with questions used in the Tobacco Use Supplement to the 2006 Current Population Survey and PATH study as well as additional standardized assessment questionnaires as described below and in Table 3. Participants will be instructed to smoke as usual until their Baseline 0 visit.

**Baseline Phase 1 (usual brand cigarette):** During this baseline period (1-3 weeks), we will collect online daily smoking diaries. Upon the participant's visit to the clinic after 1-3 weeks of usual use, we will collect additional subjective measures of use as well as collection of urine, blood, saliva, and oral cells for biomarker analysis; thus, we will establish participants' baseline smoking behavior in this phase.

**Baseline Phase 2 (Randomization & Sampling):** Immediately following the baseline assessment, participants will be randomized to one of three arms for a period of 12 weeks: 1) LWD EC, 2) HWD EC, or 3) usual brand cigarette control (UBC). Randomization will occur using a stratified block-randomization procedure with small, random-sized blocks. Randomization will be stratified by self-reported level of nicotine dependence, educational attainment, sex and age. Consistent with several of our recently completed and ongoing EC studies and to more closely mimic real-world use, those randomized to LWD or HWD will first sample five 0mg nicotine EC flavors (tobacco, mint/menthol, bakery/dessert, fruit, tobacco) to determine participants' flavor preference during the Randomized Product Trial Phase. Specific flavors across the six categories above will be determined with the most recently available data from our ongoing survey studies of EC users. After the participant selects a preferred flavor, the participant will then sample various concentration levels of the preferred e-liquid flavor. For LWD, concentrations sampled will be 6mg (extra low), 12mg (low), 18mg (medium) and 24mg (high) and for HWD, concentrations sampled will be 3mg (extra low), 6mg (low), 12mg (medium) and 18mg (high). For LWD, we still start nicotine concentration sampling at 18mg and for HWD, we will start nicotine concentration sampling at 12mg. If a participant prefers to not try a specific flavor and/or nicotine concentration, they can choose not to sample them. If a participant finds that the initial concentration (medium) they sample is not tolerable, we will not have the participant sample the highest nicotine concentration and ask them to sample the low and extra low nicotine concentrations. Participants will be asked demonstrate they know how to use the device after sampling procedures are completed. Consistent with our previous studies, participants will be instructed on how to use both the LWD or HWD products, provided a starter kit as well as ~30mL of e-liquid. The amount provided to participants will be documented and tracked throughout the study. Provision of refill cartridges or childproof bottles will be titrated up or down based on use. All products will be given to participants in their original packaging, with manufacturers' marketing, instructions, and recommendations for use and provided at no cost. We will supplement these instructions with additional information on storing the EC and all liquid and cartridges up and away from children and pets. Although overdose or accidental ingestion is very unlikely and has not occurred in [name] previous studies, all participants will be provided the state and national poison control telephone line as well as a "tip sheet" on recognizing signs of nicotine overdose.

### Examination of First and Second Generation E-cigarettes

**Randomized Product Trial Phase:** The purpose of this 12-week phase will be to assess the effect of provision of LWD vs. HWD on product uptake and use, smoking behavior, and nicotine dependence, as well as level of toxicant exposure and physiological effect. Participants randomized to LWD vs. HWD will be asked to attempt to completely switch to the product for the next 12 weeks; otherwise they will be instructed to use ad libitum. Those randomized to UBC will be instructed to use the product ad libitum. All products, to which participants will be randomized, will be provided at no cost; usual brand of cigarettes will be provided based on the average amount used per week collected during baseline phase 1. Follow-up study visits will occur at +1, +4, +8, and +12 weeks. At follow-ups, all unused product cartridges and refill bottles will be collected to account for reported use and a portion, in addition to the EC devices themselves, will also be used for subsequent HPHC analysis (see Biomarkers of Toxicant Exposure section). New cartridges and new liquid refill bottles will also be provided based on estimated use. Study visits will include completion of computerized questionnaires and collection of urine and exhaled breath samples for biomarker analysis (see Table 3 for measures collection schedule). All participants will also be asked to complete a brief (<2 minute) daily online smoking/product diary in a secure database via REDCap for the 12 weeks of product provision. Since e-liquid will no longer be provided at the end of the product trial phase, participants will be provided with a list of vape shops located in the Columbus, OH area.

**Surveillance Phase:** The purpose of this 40-week period is to assess how LWD vs. HWD use evolves over time; specifically, continued use of product assigned, transitions to other types of EC products, smoking behavior and patterns, as well as continued monitoring of biomarkers of toxicant exposure and effect over the long-term. During this phase, follow-up study visits will occur at +26 and +52 weeks, and will continue to include computerized questionnaires as well as collection of biomarkers. However, use of the daily online diary will be reduced to only the week prior the 26- and 52-week visits. Participants will be given atomizers throughout the enrollment period but will not be provided ECs, e-liquid or conventional cigarettes during this phase. Use of both will continue to be tracked. Those continuing to use any tobacco or EC product at the end of the surveillance phase will be strongly advised to quit smoking/vaping and provided the number to the Ohio Tobacco Helpline and other local smoking cessation resources.

### Counseling

Counseling as to use or not use the product at follow-up visits will not be a part of this study. At the second visit, participants randomized to ECs will be asked to attempt to completely switch to the product for the next 3 months. In subsequent visits, we will continue to ask participants to completely switch/stay switched but will not provide additional counseling (e.g., coping skills) so as to not influence the natural outcomes of product use (or non-use). For example, we assume that for those who find the product unhelpful in managing cravings or otherwise unsatisfying they will move on to another product or return to smoking. In real world use, most who try EC will not have access to a trained therapist who can effectively help them problem-solve such issues. We will provide participants trouble-shooting tips for the mechanics of their product, provide replacement parts as needed, and also address adverse events as they arise (though <2% and mild in [name] previous EC studies), but will not offer ways (e.g., timing, puff duration, etc.) to make the EC a better substitute or its use a more satisfying experience.

### Protocol Adherence and Quality Control

## Examination of First and Second Generation E-cigarettes

All research staff will have completed Human Subjects and HIPAA training. Standard operating procedures (SOP) will be developed and all staff will be trained to ensure adherence to the SOP. As is standard practice for our team's current studies, each visit will have its own checklist of specific measures to be completed and the order in which they are to be administered. To reduce data entry errors, we will use secure computer-based questionnaires for participants to complete, including daily diaries. All specimens collected for biomarker analysis will be given individualized logging codes for each participant. All key on-site personnel will meet face-to-face weekly throughout the entire study. Off-site investigators will also participate in these weekly meetings during the first year for project start-up; however, this will be reduced to every other week as the study progresses. During these meetings, recruitment, enrollment, data collection, data monitoring results, and any concerns or issues that may arise will be discussed. We will also plan for all key personnel to meet at the OSU site in the first year for start-up and then in the final year to discuss analyses, manuscripts, and future research based off of this study.

## Measures

All measures, with the exception of the daily online diary, will be collected at the study site during the eight visits as indicated in Table 3. All measures, including daily diary, have been used previously by our team and are validated, unless otherwise noted. Biomarkers of exposure and effect were chosen because they have shown reasonable laboratory reproducibility, have clear differences in levels between smokers and nonsmokers, demonstrate a dose-response relationship, and/or decrease upon tobacco cessation.

## Outcome Measures

The following outcome measures will be assessed during study visits or emailed to the study participant if they are not able to attend a visit: 1) Complete Substitution will be defined as ≥7 days of no more than 1 conventional cigarette smoked (assessed via the *Timeline Follow Back Questionnaire* that assesses all tobacco/nicotine products used for prior 7 days), exhaled carbon monoxide of <4ppm (see biomarker measures below), and reported use of ECs over the same 7-day period; 2) EC Dependence will be assessed using an adapted version of the *Cigarette Dependence Scale* and the *Penn State EC Dependence Scale*; 3) Cigarette Dependence will be measured with the *Cigarette Dependence Scale*; 4) EC Likeability/Preference will be measured using items derived from the *Cigarette Evaluation Scale* (7-point Likert-type scale assessing different dimensions of responses to EC (e.g., psychological reward, satisfaction, and averseness) and an EC adapted version of the *Product Evaluation Scale*; 5) EC Abuse Liability will be assessed using both the *Drug Effects/Liking Questionnaire* as well as the *Cigarette Purchase Task* (modified to assess amount willing to pay across similar units of product, "How much would you be willing to pay for...a pack of your usual brand of cigarettes?...one e-cigarette cartridge?...1mL of e-liquid?"); 6) Transitions to other style of EC and tobacco products will be assessed by asking participants, "Have you tried any other e-cigarette devices since your last visit?" Affirmative responses will be followed-up with questions regarding type of product, frequency and duration of use; 7) Motivation Rulers: importance, confidence, and readiness to quit smoking and to quit all nicotine products (6-items total) will be collected to assess for changes in motivation over time.

All participants will complete a daily online diary of EC and/or conventional cigarette use during the Baseline and Randomized Product Trial Phases; during the Surveillance Phase, participants will be asked to complete daily diaries the week prior to their +26 and +52-week visit. E-mails or text messages, with a link to an online survey, will be sent automatically and participants will enter data directly into a secure database (REDCap) and to encourage completion, participants will be compensated for diary completion at their next clinic visit. The participant's preferred method of contact for receiving daily diaries will be observed;

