## Examination of First and Second Generation E-cigarettes

### A. Specific Aims

The 2009 Family Smoking Prevention and Tobacco Control Act granted the FDA's Center for Tobacco Products regulatory authority over tobacco-based products. However, the FDA only recently proposed deeming regulations on e-cigarettes (ECs). Since their market emergence, ECs have evolved from low-wattage devices (LWD) which look like conventional cigarettes, have few design components and limited nicotine delivery, to high-wattage devices (HWD) which do not look like conventional cigarettes, have multiple design components and can achieve cigarette-like levels of nicotine-delivery. Each step of the evolution has led to increased consumer momentum, as well as increased demand from health officials to establish a science base to answer the question, "Are e-cigarettes a benefit or burden to public health?"

Our own as well as others' research is beginning to suggest that very few exclusive EC users use LWD products. However, for a majority of current HWD users, a LWD product was the first vapor-based product they tried. In other words, the limited available data suggests that LWDs may lead to dual use and/or serve as a gateway product to HWD products. HWD products, on the other hand, appear to be sufficient for some smokers for exclusive use—likely due, at least in part, to better nicotine delivery. Conversely, better nicotine delivery may also lead to continued long-term nicotine addiction. Moreover, HWDs may also yield more toxic and carcinogenic compounds per puff than LWDs due to higher heating of the vapor. Missing from the current literature is a prospective study assessing differences between these two major types of ECs on smoking behaviors and patterns, nicotine addiction, and on biomarkers of toxicant exposure and effect. Understanding the differential impact of LWD vs. HWD products on smoking as well as measures of proximal health outcomes will help immediately inform the science base needed for the FDA to impose appropriate product specific regulations.

**The overall aim of the proposed study is to evaluate the effect of switching from conventional cigarette smoking to one of two types of ECs on smoking behavior, product use patterns and continued use, as well as biomarkers of toxicant exposure and effects.**

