#### Aim 1:

**To assess the effect of provision of LWD vs. HWD on product switching/substitution, abuse liability, number of cigarettes smoked, and perceived nicotine dependence.** *Hypothesis 1a: Complete product substitution (vs. partial or no substitution) will occur at a significantly higher rate among smokers randomized to HWD products compared to those randomized to LWDs at 12, 26, and 52-week follow-ups. Hypothesis 1b: Compared to those randomized to UBC, LWD and HWD participants will smoke fewer cigarettes per day, have lower product abuse liability and lower perceived nicotine dependence.*

**Aim 2: To evaluate changes in biomarkers of harmful tobacco constituent exposure among participants assigned to LWD, HWD, and UBC.** *Hypothesis 2a: The degree of changes in exposure will be directly associated with the degree of substitution with EC—greater levels of substitution will confer a larger decrease in exposure to harmful constituents. Hypothesis 2b: Among those who completely substitute ECs for conventional cigarettes, LWD users (vs. HWD) will have significantly lower levels of biomarkers of exposure.*

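### At weeks 26 and 52 the complete-substitution endpoint does not separate people who have left both cigarettes and e-cigarettes from continuing smokers, and at every visit it places no limit on non-combusted tobacco

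*Combined protocol and SAP*

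**What the plan says.** Item 1 of Outcome Measures sets three joint conditions: "Complete Substitution will be defined as ≥7 days of no more than 1 conventional cigarette smoked", "exhaled carbon monoxide of <4ppm", "and reported use of ECs over the same 7-day period". Any EC counts, not only the assigned device. The cigarette count comes from the Timeline Follow-Back, which "assesses all tobacco/nicotine products used for prior 7 days", but the definition sets no limit on products other than conventional cigarettes.

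The Power Analysis makes complete substitution, LWD against HWD, the primary outcome and powers it at 3 months. Aim 1 and the Data Analytic Plan test it at weeks 12, 26 and 52: "Complete product substitution (vs. partial or no substitution) will occur at a significantly higher rate among smokers randomized to HWD products". Everyone who does not meet the definition is in the remaining class.

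Weeks 26 and 52 fall in the 40-week Surveillance Phase. Participants receive atomizers but "will not be provided ECs, e-liquid or conventional cigarettes during this phase". No section gives a separate category or a sensitivity analysis for people using neither product.

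Hypotheses 2b and 3b are analysed only among LWD and HWD participants who completely switch.

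**The concern.** **Leaving both products.** A participant who is CO-verified off cigarettes and has also stopped vaping fails the EC-use condition. In Hypothesis 1a that person is pooled with people who went back to smoking. While product is supplied, this is a natural feature of a substitution endpoint. After supply ends, the class mixes two very different outcomes, and one of them is what the Surveillance Phase text advises at study end. If the two arms differ in how many ex-smokers keep vaping, Hypothesis 1a can show a difference at weeks 26 and 52 with no difference in leaving cigarettes. It can also hide or shrink a real one. A reader would take the result as showing which device better replaces smoking.

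**Other tobacco.** The eligibility criteria do not exclude users of other tobacco. Someone who replaces cigarettes with smokeless tobacco, which would not raise CO, and reports any EC use meets all three conditions. That person enters the completely-switched subset. In Hypothesis 2b, tobacco-derived NNAL and NNN would then be attributed to the EC. In Hypothesis 3b the same person contributes to the DNA-damage comparison.

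**Working it through.** **1. The plan's own figure.** Inputs from the Power Analysis: 15% against 30%, two-sided .05 chi-squared test, about 80% power, 20% attrition, 151 per arm (453 in total), 363 evaluable. A two-proportion calculation with pooled variance and no continuity correction gives 121 per arm, and 3 × 121 = 363. Power with 121 per arm is 80.2%. 121 / 0.80 = 151.25, against 151 stated. The figure reproduces, and the point here does not depend on it.

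**2. Formula.** Let s be the proportion off cigarettes and r the proportion of those still vaping. The endpoint reads p = s × r. With n per arm, d = |p1 − p2| and p̄ = (p1 + p2)/2:

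- SE0 = √[2p̄(1 − p̄)/n]
- SE1 = √{[p1(1 − p1) + p2(1 − p2)]/n}
- P(p<.05) = Φ[(d − 1.96·SE0)/SE1] + Φ[(−d − 1.96·SE0)/SE1]

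**3. No difference in leaving cigarettes.** The documents give no value for s or r after week 12, so these are assumptions: s = 25% in both arms and r = 90% in HWD, so HWD reads 0.25 × 0.90 = 22.5%. n = 121.

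| r in LWD | LWD endpoint | HWD endpoint | P(p<.05) |
|---|---|---|---|
| 90% | 22.5% | 22.5% | 5% |
| 80% | 20.0% | 22.5% | 8% |
| 70% | 17.5% | 22.5% | 16% |
| 60% | 15.0% | 22.5% | 32% |
| 50% | 12.5% | 22.5% | 54% |

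Last row in full: d = 0.100, p̄ = 0.175, SE0 = 0.0489, SE1 = 0.0484. (0.100 − 1.96 × 0.0489)/0.0484 ≈ 0.09, which gives 0.535; the second term is negligible. Swapping the arms gives the same probabilities in favour of LWD.

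**4. A real difference.** Take smoke-free rates of 15% (LWD) and 30% (HWD), again with 121 per arm and assumed shares.

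- 20% of ex-smokers have stopped vaping in both arms: 12% against 24%, power 68.3%, down from 80.2%.
- 10% have stopped in LWD and 30% in HWD: 13.5% against 21%, power 33.8%.
- 30% have stopped in LWD and 10% in HWD: 10.5% against 27%, power 91.3%.

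The EC-use condition can therefore create, shrink or enlarge an arm difference, depending on quantities the plan does not report.

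**5. Other tobacco.** The documents give no prevalence. If 1 to 5 percentage points of such users are added equally to both arms, power at 15% against 30% moves from 80.2% to between 78.9% and 74.6%, so Hypothesis 1a is little affected. The 2b/3b subset is small: at the planning rates it would hold about 0.15 × 121 ≈ 18 LWD and 0.30 × 121 ≈ 36 HWD participants, so one such user is about 1/18 = 5.6% of the LWD side. The questionnaire items listed for biomarker adjustment cover tobacco smoke exposure at home, work and socially, alcohol and drugs, stress, respiratory symptoms and medications. A participant's own use of other tobacco is not among them.

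**The case against.** The strongest reply is that EC use is the construct. Hypothesis 1a concerns substitution, the overall aim includes continued product use, and supply is withdrawn deliberately to see what people then do. Someone using neither product is not substituting. This stands: the definition is not an error, and people outside it are not misclassified with respect to what it names. What remains is that the comparison class is not split and no smoke-free rate regardless of EC use is planned.

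Second, other outcomes cover part of the gap. Cigarettes per day is modelled to 12 months with two arm indicators, so an LWD-HWD contrast can be estimated, and nicotine equivalents, dependence and motivation to quit all nicotine are collected. This partly stands. Hypothesis 1b is framed against usual-brand cigarettes, and a mean count does not separate users of neither product from smokers.

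Third, a reader might infer that the endpoint is biased towards HWD, because the Specific Aims say "better nicotine delivery may also lead to continued long-term nicotine addiction". The documents do not support that step. They do not say that smoke-free LWD users stop vaping more often. They suggest LWDs may lead on to HWDs, and any EC counts. The Counseling section expects dissatisfied users to try another product or resume smoking, and enrolment is limited to smokers not planning to quit in the next 3 months. The group using neither product may be small.

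Fourth, CO below 4 ppm should remove much recent use of other combusted tobacco. This also stands, and narrows the second part to non-combusted products.

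**Conclusion.** The point holds in limited form. At weeks 26 and 52, a Hypothesis 1a difference cannot by itself be read as a difference in leaving cigarettes, because it also depends on continued vaping after supply ends. The direction and size are unknown from the documents. The 5% to 54% range rests wholly on the assumed 25% off cigarettes, 90% HWD retention and 121 analysed per arm, and reversed retention would favour LWD.

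The no-supply argument does not reach the powered week-12 comparison, and a reader should not conclude that the primary analysis is invalid. Nor does the trial overlook other tobacco in data collection: the Timeline Follow-Back records it, and only the definition leaves it out. That gap matters mainly for the small 2b/3b subset, and its size cannot be given. Both parts are worth settling before analysis, since they affect what may be claimed and cost little.

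**What to change.** Keep the present endpoint for Hypothesis 1a at all visits, and add the following to Outcome Measures and the Data Analytic Plan.

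1. At weeks 26 and 52, classify each participant as EC only, dual use, cigarettes only, or neither, and report all four by arm.
2. At the same visits, compare LWD and HWD on smoke-free status regardless of EC use (no more than 1 cigarette in 7 days and CO below 4 ppm), using the Hypothesis 1a model and missing-data approach, with a confidence interval.
3. State in advance that a Hypothesis 1a difference at those visits will be interpreted as better replacement of smoking only if the smoke-free estimate lies in the same direction, and otherwise as a difference in continued EC use. The condition concerns the direction of the estimate, not its significance.
4. For Hypotheses 2b and 3b, restrict the completely-switched subset to participants whose Timeline Follow-Back shows no other combusted or oral tobacco in the same 7 days. Repeat Hypothesis 1a with that condition as a sensitivity analysis.

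The Timeline Follow-Back and CO are already needed for the endpoint, so no new visit, sample or questionnaire is required. The cost is one companion endpoint and a slightly smaller 2b/3b subset.
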